5.4 Duration of Therapy

In the absence of treatment delays due to adverse event(s), treatment may continue for up to 46 doses in Cohort A or until one of the following criteria applies. In Cohort B, treatment may continue for up to 4 doses of combination therapy (nivolumab + ipilimumab), and up to 46 doses of nivolumab monotherapy after the combination therapy, or until one of the following criteria applies:

- Disease progression, as per section 5.9
- Intercurrent illness that prevents further administration of treatment,
- Any patients who require additional immune suppressive treatment beyond steroids should go off study treatment
- Unacceptable adverse event(s) which include the following (see also section 6 and

specific algorithms in Appendix E):

- Any grade 2 drug-related uveitis or eye pain or blurred vision that does not respond to topical therapy and does not improve to Grade 1 severity within the re-treatment period OR requires systemic treatment
- Patients requiring > two dose delays for the same type of event should go off protocol therapy.
- Any adverse event, laboratory abnormality, or intercurrent illness which, in the judgment of the investigator, presents a substantial clinical risk to the subject with continued study drug dosing
- Any dosing interruption lasting >6 weeks, with the following exceptions:
- Patients being tapered after high dose corticosteroids over one month followed by a two-week observation period will be allowed an additional two weeks to restart treatment (a maximum eight week interruption).
- Dosing interruptions >6 weeks that occur for non-drug-related reasons may be allowed if approved by the Investigator. Prior to re-initiating treatment in a subject with a dosing interruption lasting >6 weeks, the Principal Investigator must be consulted.
- Grade 3 drug-related autoimmune or inflammatory events including uveitis, pneumonitis, diarrhea, colitis, neurologic adverse events, hypersensitivity reaction, or infusion reaction of any duration requires discontinuation except as noted below:
- Any other grade 3 non-skin, drug-related AE lasting >7 days including fatigue.
- Any grade 3 or 4 drug-related laboratory abnormality or electrolyte abnormality, not associated with underlying organ pathology, that does not require treatment except for electrolyte replacements **does not** require treatment discontinuation.

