5.7 Criteria to Resume Treatment

Management of adverse events is summarized in section 6 and may include holding of nivolumab and ipilimumab, and/or the use of steroids for the management of immune related AEs.

If drug administration is held until the next scheduled time point, please continue to count weeks/doses. If patients must be delayed due to toxicity, all assessments can be obtained with the modified treatment dose schedule as noted in this section.

Some patients may continue to benefit from treatment, maintaining or improving responses after progression including those treated with steroids.

Restarting nivolumab may be considered in patients who experience grade 2 events and some grade 3 events (skin rash and thyroiditis). Because of this, stopping treatment and starting steroids earlier, as per section 6, to obtain resolution with the possibility for restarting rather than waiting for higher grade events is encouraged.

For non-autoimmune or non-inflammatory events patients may resume treatment with study drug when the drug-related AE(s) resolve to Grade ≤ 1 or baseline value, with the following exceptions:

- Evaluation to exclude any additional immune mediated events endocrine, GI, and liver / pancreas function as clinically indicated must be made prior to restarting.
- Non-drug-related toxicity including hepatic, pulmonary toxicity, diarrhea, or colitis, must have resolved to baseline before treatment is resumed.

If the criteria to resume treatment are met, the patient should restart treatment no sooner than the next scheduled time point per protocol. However, if the treatment is delayed past the next scheduled time point per protocol the treatment should resume at the earliest convenient point that is within the six week delay period.

For protocols using combination nivolumab/Ipilimumab for the initial induction period patients with grade 2 or 3 events requiring discontinuation of treatment with the combination, the PI may consider continuing treatment with single agent nivolumab at the same dose when the event resolves to baseline. However, patients with renal, CNS, or pulmonary toxicity must be removed from study.

For patients treated with corticosteroids:

For patients treated with high dose steroids with nivolumab/Ipilimumab, toxicity must resolve to baseline within 8 weeks of treatment.

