Patients should be off steroids for at least 2 weeks with no recurrence or new events. New immune related events or exacerbation of existing events during steroid treatment or taper suggest the presence of ongoing immune activation and should require permanent discontinuation of nivolumab.

Grade 2 events must resolve to grade ≤ 1 before considering retreatment.

All patients treated with steroids for grade ≥ 2 events should have nivolumab held until resolution to grade ≤ 1 for at least 2 weeks following complete removal from steroid treatment except for maintenance replacement doses for adrenal insufficiency (preferably no greater than 10mg prednisone equivalent daily).

All patients treated with steroids for grade ≥ 3 events should have nivolumab discontinued. Patients with grade 3 thyroiditis and skin rash may continue therapy as for grade 2 events with resolution and stable replacement treatment.

Patients with hepatitis, pancreatitis, pneumonitis, and colitis are at risk for exacerbation with retreatment if there is residual inflammation and should resolve to Grade 0 or baseline before retreatment. Baseline can mean the initial grade *i.e.* grade <1 where permitted on study.

Patients with thyroiditis or hypopituitarism who are stable as above may be restarted with replacement hormones including thyroid hormone and physiologic doses only of corticosteroids. Please note that grading and for hypophysitis with symptoms of headache, visual or neurologic changes or radiologic evidence of pituitary enlargement and other CNS events such as aseptic meningitis or encephalitis should be considered grade 3 events.

New immune related events or exacerbation of existing events during steroid treatment or taper suggest the presence of ongoing immune activation and should require permanent discontinuation of nivolumab.

A patient who is treated with steroids, evaluated, and found to not have an autoimmune or inflammatory event requiring steroid treatment, may be restarted if asymptomatic off steroids for 2 weeks and other restarting criteria are met.

Prior to starting corticosteroids or hormone replacement for any reason, appropriate endocrine

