| ≤ Grade 1 | Evaluate and continue treatment at same level at investigator discretion. |
| Grade 2 | Hold until Grade ≤1 or baseline following treatment algorithm; evaluate and resume at investigator discretion if additional therapy is not required. |
| Grade 3 | Hold until Grade ≤1 or baseline following treatment algorithm; evaluate and resume at investigator discretion. |
| Grade 4 | Off protocol therapy |
| See GI AE Algorithm for management of symptomatic colitis. Patients with grade 2 symptoms but normal colonoscopy and biopsies may be retreated after resolution. Please evaluate pituitary function prior to starting steroids if possible without compromising acute care. Evaluation for all patients for additional causes includes C. diff , acute and self-limited infectious and foodborne illness, ischemic bowel, diverticulitis, and IBD. | |
| Recommended management: see GI AE management Algorithm | |

| Pancreatitis Amylase/Lipase | Management/Next Dose for Nivolumab and combination Nivolumab/ipilimumab |
|--|---|
| ≤ Grade 1 | Continue treatment at same level at investigator discretion. |
| Grade 2 | Continue treatment at same level at investigator discretion if asymptomatic. |
| Grade 3 | Hold until Grade ≤2 . Resume at same dose level if asymptomatic. Patients who develop symptomatic pancreatitis or DM should be taken off treatment. |
| Grade 4 | Hold until Grade ≤2 . Resume at same dose level if asymptomatic. Patients who develop symptomatic pancreatitis or DM should be taken off treatment. |
| Patients may develop symptomatic and radiologic evidence of pancreatitis as well as DM and DKA. Lipase elevation may occur during the period of steroid withdrawal and with other immune mediated events or associated with colitis, hepatitis, and patients who have asymptomatic lipase elevation typically have self-limited course and may be retreated. For treatment management of symptomatic pancreatitis please follow the Hepatic Adverse Event Management Algorithm. | |

| Pneumonitis | Management/Next Dose for Nivolumab and combination Nivolumab/ipilimumab |
|--|---|
| ≤ Grade 1 | Hold dose pending evaluation and resolution to baseline including baseline pO ₂ . Resume no change in dose after pulmonary and/or ID consultation excludes agent associated lymphocytic pneumonitis. |

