| Grade 2 | Hold dose pending evaluation. Resume no change in dose after pulmonary and/or ID consultation excludes nivolumab/ipilimumab associated lymphocytic pneumonitis As the cause of the pneumonitis. Off study if steroids are required. |
| Grade 3 | Hold dose pending evaluation. Resume no change in dose after pulmonary and/or ID consultation excludes nivolumab/ipilimumab associated lymphocytic pneumonitis as the cause of the pneumonitis. Off study if steroids are required. |
| Grade 4 | Off protocol therapy |
| Distinguishing inflammatory pneumonitis is often a diagnosis of exclusion for patients who do not respond to antibiotics and have no causal organism identified including influenza. Most patients with respiratory failure or hypoxia will be treated with steroids. Bronchoscopy may be required and analysis of lavage fluid for lymphocytic predominance may be helpful. Patients with new lung nodules should be evaluated for sarcoid like granuloma. Please consider recommending seasonal influenza killed vaccine for all patients. | |
| Recommended management: See Pulmonary Adverse Event Management Algorithm | |

| Other GI N-V | Management/Next Dose for Nivolumab and combination Nivolumab/ipilimumab |
|---|---|
| ≤ Grade 1 | No change in dose. |
| Grade 2 | Hold pending evaluation for gastritis duodenitis and other immune adverse events or other causes. Resume at investigator discretion. |
| Grade 3 | Hold pending evaluation until ≤ Grade 2. Resume at same dose level. If symptoms do not resolve within 7 days with symptomatic treatment patients should go off protocol therapy |
| Grade 4 | Off protocol therapy |
| Patients with grade 2 or 3 N-V should be evaluated for upper GI inflammation and other immune related events. | |

| Fatigue | Management/Next Dose for Nivolumab and combination Nivolumab/ipilimumab |
|---|--|
| ≤ Grade 1 | No change in dose. |
| Grade 2 | No change in dose |
| Grade 3 | Hold until ≤ Grade 2. Resume at same dose level at investigator discretion. |
| Grade 4 | Off protocol therapy |
| Fatigue is the most common adverse event associated with immune checkpoint therapy. Grade 2 or greater fatigue should be evaluated for associated or underlying organ involvement including pituitary, thyroid, and hepatic, or muscle (CPK) inflammation | |

| Cardiac * | Management/Next Dose for BMS-936558 (Nivolumab) + Ipilimumab Cardiac Toxicities |
|-------------------------------------|---|

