| ≤ Grade 1 | Asymptomatic TSH elevation*; continue at investigator discretion with evaluation of thyroid function. |
| Grade 2 | Hold until patients are on a stable replacement hormone regimen. If treated with steroids, patients must be stable off steroids for two weeks. Resume at same dose level. |
| Grade 3 | Off protocol therapy. |
| Grade 4 | Off protocol therapy |
| 
Note all patients with symptomatic pituitary enlargement, exclusive of hormone deficiency, but including severe headache or enlarged pituitary on MRI should be considered grade 3 events. Isolated thyroid or testosterone deficiency may be treated as grade 2 if there are no other associated deficiencies and adrenal function is monitored.
 
Please evaluate pituitary function before beginning steroid therapy or replacement therapy of any kind.
 
*Note patients with thyroiditis may be retreated on replacement therapy. Patients must be evaluated to rule out pituitary disease prior to initiating thyroid replacement.
 | |
| 
Recommended management: TSH, T3, and T4 will be collected at baseline. After baseline, TSH will be collected every 6 weeks; T3/T4 will be collected when indicated. See Endocrine Management Algorithm
 | |

| Renal | Management/Next Dose for Nivolumab and combination Nivolumab/ipilimumab |
|--|--|
| ≤ Grade 1 | Continue at same dose at investigator discretion |
| Grade 2 | Hold pending evaluation. Resume at same dose level at investigator discretion. |
| Grade 3 | Off study treatment |
| Grade 4 | Off study treatment |
| 
Patients with fever should be evaluated as clinically appropriate. Patients may experience isolated fever during infusion reactions or up to several days after infusion. Evaluation over the course of 1-2 weeks should be done for other autoimmune events that may present as fever
 | |
| Infusion reaction | Management/Next Dose for Nivolumab and combination Nivolumab/ipilimumab |
| ≤ Grade 1 | Continue at slower rate at investigator discretion |
| Grade 2 | Hold until ≤ Grade 1. Resume at same dose level |
| Grade 3 | Hold until ≤ Grade 1. Resume at same dose level |
| Grade 4 | Off protocol therapy |

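### Two Grade 3 rows in Section 6 (diarrhea/colitis and infusion reaction) allow drug to resume where Section 5.4 requires discontinuation

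*Combined protocol and SAP*

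**What the plan says.** **Section 6, Diarrhea/Colitis, Grade 3.** Hold until Grade ≤1 "or baseline following treatment algorithm; evaluate and resume at investigator discretion". The column covers nivolumab alone and the combination.

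**Section 6, Infusion reaction.** "Grade 3 | Hold until ≤ Grade 1. Resume at same dose level". The table refers the reader to 5.8.

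**Section 5.4.** Among Grade 3 drug-related autoimmune or inflammatory events, the stop list includes "diarrhea, colitis, neurologic adverse events, hypersensitivity reaction, or infusion reaction of any duration requires discontinuation except as noted below".

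**Section 5.7** has four rules that bear on this:
- General restart rule: "Restarting nivolumab may be considered in patients who experience grade 2 events and some grade 3 events (skin rash and thyroiditis").
- Steroid-treated cases of Grade 3 or higher: "events should have nivolumab discontinued. Patients with grade 3 thyroiditis and skin rash may continue therapy as for grade 2 events".
- Events not caused by drug: "Non-drug-related toxicity including hepatic, pulmonary toxicity, diarrhea, or colitis, must have resolved to baseline before treatment is resumed".
- Grade 2 or 3 events that end the combination: "the PI may consider continuing treatment with single agent nivolumab at the same dose when the event resolves to baseline". Renal, CNS and pulmonary toxicity are shut out of this option; bowel toxicity is not.

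**Section 5.8.** After a Grade 3 or 4 infusion reaction, nivolumab is stopped for good.

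**Section 6, text after the tables.** Patients who need high-dose steroids for immune events are to be managed under 5.7, apart from short tapering courses for infusion reaction, rash or endocrine events. Anyone who needs immunosuppression beyond steroids leaves protocol therapy.

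**The concern.** These rows decide whether a patient is re-exposed to checkpoint inhibitors after a severe immune bowel event or a severe infusion reaction. On the same event, 5.4 stops treatment and the table permits it to resume. A site working from the table can therefore reach a different decision from a site working from 5.4. The adverse event lists in Section 7.1 include colonic perforation for both agents, so re-exposure after Grade 3 colitis is a real safety matter.

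Section 6 elsewhere suggests that the permission was not intended. Its general table for immune-mediated events takes Grade 3 off therapy and defers to 5.4 for exceptions. Its pneumonitis rows, at Grade 2 and in near-identical words at Grade 3, limit restart by cause: "Resume no change in dose after pulmonary and/or ID consultation excludes nivolumab/ipilimumab associated lymphocytic pneumonitis As the cause of the pneumonitis". The Grade 2 colitis row allows restart only if no further therapy is needed, a condition that is missing at Grade 3.

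**Working it through.** No rate or power calculation applies. The check sets the rules side by side, with one dose count.

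**Step 1. Does any 5.4 exception cover colitis?** The text after the stop rule contains two true exceptions: laboratory or electrolyte abnormalities without organ pathology, and amylase or lipase elevations. The item on other Grade 3 non-skin drug-related events lasting more than 7 days is a further reason to stop, not an exception. Colitis is not excepted.

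**Step 2. Grade 3 diarrhea/colitis by cause.**

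| Case | 5.4 | 5.7 | Section 6 | Result |
|---|---|---|---|---|
| Immune, drug-related, high-dose steroids | Stop | Nivolumab stopped | Row permits restart; later text sends the case to 5.7 | Row is wrong as written, but Section 6 leads to a stop |
| Immune, drug-related, no high-dose steroids | Stop | Stopped if any steroid was given for it; otherwise not among the restartable Grade 3 events, but the single-agent option may apply on the combination | Row permits restart of both drugs | **Open conflict** |
| Drug-related, not inflammatory | Stop if longer than 7 days | Restart at Grade ≤1 or baseline | Restart at Grade ≤1 or baseline | Consistent, apart from the 7-day stop |
| Not drug-related | Not in this rule | Baseline | Grade ≤1 or baseline | Waiting for baseline satisfies both |

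For colitis, the open conflict lies in the second line.

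**Step 3. Ipilimumab doses at issue in Cohort B.** Section 5.4 allows 4 combination doses. For an event after combination dose k, the row permits at most 4 − k further ipilimumab doses:
- k = 1: 4 − 1 = 3
- k = 2: 4 − 2 = 2
- k = 3: 4 − 3 = 1
- k = 4: 4 − 4 = 0

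Section 5.4 permits 0 in each case. So does the 5.7 option, because it continues nivolumab alone. The row and the 5.7 option differ in three ways: who decides (investigator or PI), the level of recovery (Grade ≤1 or baseline, against baseline), and ipilimumab. Section 5.4 does not list the option as an exception, so those two sections also need reconciling.

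**Step 4. Infusion reaction, Grade 3.** 5.4: stop. 5.8: nivolumab permanently stopped. Section 6 row: resume at the same dose after recovery to Grade ≤1. The redirect to 5.7 is no help here, because it excepts short steroid tapers for infusion reactions.

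**Step 5. Cross-references.** The opening of Section 6 twice sends the reader to 5.6 for restart rules. Section 5.6 covers removal from study; the restart rules are in 5.7. The later steroid text in Section 6 cites 5.7 correctly.

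**The case against.** The strongest reply is that the sections are meant to be read together. Section 5.4 points to Section 6. The colitis row is permissive and 5.4 is mandatory, so a site applying both has one compliant answer, which is to stop. Patients on high-dose steroids are already sent to 5.7. The row also says to follow the treatment algorithm, and its table note asks for other causes to be evaluated in every patient. Section 5.7 is not uniformly strict either, since it lets the PI continue nivolumab alone after a Grade 3 event on the combination.

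Much of this stands. It narrows the colitis conflict to the second line of the table and the ipilimumab permission. It does not remove it:
- The note asks for evaluation but does not bar restart when the cause proves to be immune.
- No text says which section governs.
- The permissive-versus-mandatory argument does not make the infusion row correct. That row gives a plain instruction to resume, against two other sections.

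Three stronger readings are tempting and are not supported:
- *A reader might infer that Section 6 makes sites re-treat Grade 3 immune colitis.* It permits restart but does not order it, and the GI algorithm that the row relies on is a figure not shown.
- *A reader might set no further treatment under 5.4 against the full remaining nivolumab course under the row.* The 5.7 option also lets nivolumab continue for some Cohort B patients, so the clean contrast is in ipilimumab doses.
- *A reader might single out the colitis row as the one faulty row.* The infusion row has the same defect.

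The wrong cross-reference is clerical. Section 5.6 itself leads back to the criteria in 5.4, so it adds little harm.

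**Conclusion.** The point holds as a conflict between the visible texts in two Grade 3 rows. For infusion reactions it is direct. For diarrhea/colitis it is mainly confined to drug-related immune events managed without high-dose steroids, plus the permission to restart ipilimumab: at most 3 further doses after an event at dose 1, against none under 5.4. That count is a ceiling, since other stop rules may end treatment sooner.

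How often this would arise cannot be stated, because the documents give no Grade 3 drug-related colitis rate for the Cohort B schedule. The operating characteristics in Section 13.1 take no input from these rows and are unaffected. The conclusion assumes that 5.4 and 5.8 state the intended rule, which the general immune-event table in Section 6 supports. It makes no claim about what sites do or did. The rows should be corrected because they govern re-exposure after severe toxicity and the correction is cheap.

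**What to change.** 1. **Grade 3 Diarrhea/Colitis row.** Replace with: drug-related autoimmune or inflammatory, off protocol therapy per 5.4; resume only when that cause is excluded, after resolution as required by 5.7. The existing 5.4 stop for other drug-related Grade 3 events lasting more than 7 days continues to apply.
2. **Section 5.4.** State whether the single-agent nivolumab option in 5.7 applies to Grade 3 colitis. If it does, list it as an exception that requires return to baseline, no steroid treatment and no further ipilimumab.
3. **Grade 3 Infusion reaction row.** Change to off protocol therapy per 5.4 and 5.8.
4. **Clerical.** Change the two references to 5.6 at the start of Section 6 to 5.7.

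The cost is a protocol amendment to two table rows, one statement in 5.4 and two cross-references, with no added assessments. The downside is that a few patients lose retreatment that the rows now allow.

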7 ADVERSE EVENTS: LIST AND REPORTING REQUIREMENTS

Adverse event (AE) monitoring and reporting is a routine part of every clinical trial. The

following list of AEs (Section 7.1) and the characteristics of an observed AE (Section 7.2) will determine whether the event requires expedited reporting via the CTEP Adverse Event Reporting System (CTEP-AERS) **in addition** to routine reporting.

7.1 Comprehensive Adverse Events and Potential Risks Lists (CAEPRs)

7.1.2 CAEPRs for CTEP IND Agent

7.1.2.1 CAEPR for Nivolumab

Comprehensive Adverse Events and Potential Risks list (CAEPR) for **BMS-936558 (Nivolumab, MDX-1106, NSC 748726)**

The Comprehensive Adverse Events and Potential Risks list (CAEPR) provides a single list of reported and/or potential adverse events (AE) associated with an agent using a uniform presentation of events by body system. In addition to the comprehensive list, a subset, the Specific Protocol Exceptions to Expedited Reporting (SPEER), appears in a separate column and is identified with **bold** and *italicized* text. This subset of AEs (SPEER) is a list of events that are protocol specific exceptions to expedited reporting to NCI (except as noted below). Refer to the 'CTEP, NCI Guidelines: Adverse Event Reporting Requirements'

http://ctep.cancer.gov/protocolDevelopment/electronic_applications/docs/aeguidelines.pdf for further clarification. *Frequency is provided based on 2069 patients.* Below is the CAEPR for BMS-936558 (Nivolumab, MDX-1106).

NOTE: Report AEs on the SPEER **ONLY IF** they exceed the grade noted in parentheses next to the AE in the SPEER. If this CAEPR is part of a combination protocol using multiple investigational agents and has an AE listed on different SPEERs, use the lower of the grades to determine if expedited reporting is required.

Version 2.2, November 15, 2016¹

| Adverse Events with Possible Relationship to BMS-936558 (Nivolumab, MDX-1106) (CTCAE 4.0 Term) [n= 782] | | | Specific Protocol Exceptions to Expedited Reporting (SPEER) |
|---|---------------------|--|---|
| Likely (>20%) | Less Likely (<=20%) | Rare but Serious (<3%) | |
| BLOOD AND LYMPHATIC SYSTEM DISORDERS | | | |
| | Anemia | | Anemia (Gr 2) |
| CARDIAC DISORDERS | | | |
| | | Cardiac disorders-other (cardiomyopathy) | |
| | | Myocarditis | |
| | | Pericardial tamponade ² | |

| | | | |
|---|--|--|---------------------------------------|
| | | Pericarditis | |
| ENDOCRINE DISORDERS | | | |
| | Adrenal insufficiency | | |
| | Endocrine disorders - Other (hypophysitis) | | |
| | Hyperthyroidism | | |
| | Hypothyroidism | | |
| EYE DISORDERS | | | |
| | | Eye disorders - Other (diplopia) | |
| | | Eye disorders – Other (Graves ophthalmopathy) | |
| | | Eye disorders - Other (optic neuritis retrobulbar) | |
| | Uveitis | | |
| GASTROINTESTINAL DISORDERS | | | |
| | Abdominal pain | | Abdominal pain (Gr 2) |
| | Colitis | | |
| | | Colonic perforation | |
| | Diarrhea | | Diarrhea (Gr 2) |
| | Dry mouth | | Dry mouth (Gr 2) |
| | | Gastritis | |
| | Nausea | | Nausea (Gr 2) |
| | Pancreatitis ³ | | |
| GENERAL DISORDERS AND ADMINISTRATION SITE CONDITIONS | | | |
| Fatigue | | | Fatigue (Gr 2) |
| | Fever | | Fever (Gr 2) |
| | Infusion related reaction ⁴ | | |
| | Injection site reaction | | Injection site reaction (Gr 2) |
| IMMUNE SYSTEM DISORDERS | | | |
| | | Allergic reaction | |
| | | Autoimmune disorder ⁵ | |
| | | Cytokine release syndrome ⁶ | |
| | | Immune system disorders - Other (GVHD in the setting of autotransplant) ⁷ | |

| | | | |
|--|--------------------------------------|--|--|
| | | Immune system disorders – Other (sarcoid granuloma) ⁵ | |
| INVESTIGATIONS | | | |
| | Alanine aminotransferase increased | | Alanine aminotransferase increased (Gr 2) |
| | Aspartate aminotransferase increased | | Aspartate aminotransferase increased (Gr 2) |
| | Blood bilirubin increased | | Blood bilirubin increased (Gr 2) |
| | Creatinine increased | | |
| | Lipase increased | | |
| | Lymphocyte count decreased | | Lymphocyte count decreased (Gr 2) |
| | Neutrophil count decreased | | |
| | Platelet count decreased | | |
| | Serum amylase increased | | |
| METABOLISM AND NUTRITION DISORDERS | | | |
| | Anorexia | | |
| | | Hyperglycemia | Hyperglycemia (Gr 2) |
| | | Metabolism and nutritional disorders - Other (diabetes mellitus with ketoacidosis) | |
| MUSCULOSKELETAL AND CONNECTIVE TISSUE DISORDERS | | | |
| | Arthralgia | | |
| | | Musculoskeletal and connective tissue disorder- Other (polymyositis) | |
| | | Musculoskeletal and connective tissue disorder- Other (rhabdomyolysis) | |
| | | Myositis | |
| NERVOUS SYSTEM DISORDERS | | | |
| | | Encephalopathy | |
| | | Facial nerve disorder ⁵ | |

| | | | |
|---|---------------------|---|-----------------------------------|
| | | Nervous system disorders – Other (demyelination myasthenic syndrome) | |
| | | Nervous system disorders – Other (encephalitis) | |
| | | Nervous system disorders – Other (Guillain-Barre syndrome) ⁵ | |
| | | Nervous system disorders - Other (meningoencephalitis) | |
| | | Nervous system disorders - Other (meningoRADICULITIS) | |
| | | Nervous system disorders – Other (myasthenia gravis) ⁵ | |
| | | Nervous system disorders - Other (myasthenic syndrome) | |
| | | Peripheral motor neuropathy | |
| | | Peripheral sensory neuropathy | |
| RENAL AND URINARY DISORDERS | | | |
| | | Acute kidney injury | |
| RESPIRATORY, THORACIC AND MEDIASTINAL DISORDERS | | | |
| | Pleural effusion | | |
| | Pneumonitis | | |
| | | Respiratory, thoracic and mediastinal disorders – Other (brochiolitis obliterans with organizing pneumonia) | |
| SKIN AND SUBCUTANEOUS TISSUE DISORDERS | | | |
| | | Erythema multiforme | |
| | Pruritus | | Pruritus (Gr 2) |
| | Rash maculo-papular | | Rash maculo-papular (Gr 2) |

| | | | |
|--|--|--|--|
| | Skin hypopigmentation | | |
| | Skin and subcutaneous disorders – Other (Sweet’s Syndrome) | | |

¹This table will be updated as the toxicity profile of the agent is revised. Updates will be distributed to all Principal Investigators at the time of revision. The current version can be obtained by contacting [contact]. Your name, the name of the investigator, the protocol and the agent should be included in the e-mail.

²Pericardial tamponade may be related to possible inflammatory reaction at tumor site.

³Pancreatitis may result in increased serum amylase and/or more frequently lipase.

⁴Infusion reactions, including high-grade hypersensitivity reactions which have been observed following administration of nivolumab, may manifest as fever, chills, shakes, itching, rash, hypertension or hypotension, or difficulty breathing during and immediately after administration of nivolumab.

⁵BMS-936558 (Nivolumab, MDX-1106) being a member of class of agents involved in the inhibition of “immune checkpoints”, may result in severe and possibly fatal immune-mediated adverse events probably due to T-cell activation and proliferation. This may result in autoimmune disorders that can include (but are not limited to) autoimmune hemolytic anemia, acquired anti-factor VIII immune response, autoimmune aseptic meningitis, autoimmune hepatitis, autoimmune nephritis, autoimmune neuropathy, autoimmune thyroiditis, bullous pemphigoid; exacerbation of Churg-Strauss Syndrome, drug rash with eosinophilia, systemic symptoms [DRESS] syndrome, facial nerve disorder (facial nerve paralysis), limbic encephalitis, hepatic failure, pure red cell aplasia, pancreatitis, ulcerative and hemorrhagic colitis, endocrine disorders (e.g., autoimmune thyroiditis, hyperthyroidism, hypothyroidism, autoimmune hypophysitis/hypopituitarism, thyrotoxicosis, and adrenal insufficiency), sarcoid granuloma, myasthenia gravis, polymyositis, and Guillain-Barre syndrome.

⁶Cytokine release syndrome may manifest as hemophagocytic lymphohistiocytosis with accompanying fever and pancytopenia.

⁷Complications including hyperacute graft-versus-host disease (GVHD), some fatal, have occurred in patients receiving allo stem cell transplant (SCT) after receiving BMS-936558 (Nivolumab, MDX-1106). These complications may occur despite intervening therapy between receiving BMS-936558 (Nivolumab, MDX-1106) and allo-SCT.

Also reported on BMS-936558 (Nivolumab, MDX-1106) trials but for which there is insufficient evidence to suggest that there was a reasonable possibility that BMS-936558 caused the adverse event:

CARDIAC DISORDERS – Atrial fibrillation; Atrioventricular block complete; Heart failure; Pericarditis; Ventricular arrhythmia

EAR AND LABYRINTH DISORDERS – Vestibular disorder

EYE DISORDERS - Eye disorders – Other (iritocyclitis); Optic nerve disorder

GASTROINTESTINAL DISORDERS - Constipation; Duodenal ulcer; Flatulence;

Gastrointestinal disorders - Other (mouth sores); Mucositis oral; Vomiting

GENERAL DISORDERS AND ADMINISTRATION SITE CONDITIONS – Chills; Edema
limbs; Malaise; Pain

HEPATOBILIARY DISORDERS – Bile duct stenosis

IMMUNE SYSTEM DISORDERS - Anaphylaxis; Immune system disorders - Other
(autoimmune thrombotic microangiopathy); Immune system disorders – Other (limbic
encephalitis)

INFECTIONS AND INFESTATIONS – Bronchial infection; Lung infection; Sepsis; Upper
respiratory infection

INVESTIGATIONS - GGT increased; Investigations - Other (blood LDH increased);
Investigations - Other (protein total decreased); Investigations - Other (WBC count increased);
Lymphocyte count increased; Weight loss

METABOLISM AND NUTRITION DISORDERS - Dehydration; Hyperuricemia;
Hypoalbuminemia, Hypocalcemia; Hyponatremia; Hypophosphatemia

MUSCULOSKELETAL AND CONNECTIVE TISSUE DISORDERS - Back pain;
Musculoskeletal and connective tissue disorder - Other (musculoskeletal pain); Musculoskeletal
and connective tissue disorder - Other (polymyalgia rheumatica); Myalgia; Pain in extremity

NEOPLASMS BENIGN, MALIGNANT AND UNSPECIFIED (INCL CYSTS AND

POLYPS) - Neoplasms benign, malignant and unspecified (incl cysts and polyps) - Other
(histiocytic necrotizing lymphadenitis)

NERVOUS SYSTEM DISORDERS - Dizziness; Headache; Intracranial hemorrhage

PSYCHIATRIC DISORDERS - Insomnia

RENAL AND URINARY DISORDERS – Hematuria; Renal and urinary disorders - Other
(tubulointerstitial nephritis)

RESPIRATORY, THORACIC AND MEDIASTINAL DISORDERS – Bronchospasm;
Cough; Dyspnea; Hypoxia

SKIN AND SUBCUTANEOUS TISSUE DISORDERS – Alopecia; Dry skin; Hyperhidrosis;
Pain of skin; Periorbital edema; Photosensitivity; Rash acneiform; Skin and subcutaneous tissue
disorders - Other (rosacea); Toxic epidermal necrolysis

VASCULAR DISORDERS – Flushing; Hypertension; Hypotension; Vasculitis

Note: BMS-936558 (Nivolumab, MDX-1106) in combination with other agents could cause an
exacerbation of any adverse event currently known to be caused by the other agent, or the
combination may result in events never previously associated with either agent.

